#### Footnotes:

- 1. Baseline assessments (including physical examination and vital signs, ECOG performance status, assessment of baseline conditions, review of concomitant medications, safety bloods, ECG): may be performed within 3 days prior to commencing trial treatment within the WOP (with the exception of Research tissue and blood samples which should be collected pre-treatment on either Day -1 or 1.
- 2. Physical examination and vital signs: To include height at prior Trial Entry only, and weight, blood pressure (BP), heart rate and temperature at all time points.
- 3. Safety bloods: Haematology full blood count, white cell count with differential and ANC, prothrombin time and international normalised ratio (INR); Biochemistry sodium, potassium, calcium, magnesium, ALT, gamma-glutamyl transferase (GGT), bilirubin, albumin, creatinine, alkaline phosphatase, glucose, urea. Hepatitis serologies (hepatitis B and C mandatory, hepatitis A as per local practice) should be performed as part of the Trial Entry screening assessments only
- 4. **Pregnancy Test:** Women of childbearing potential should have a negative serum or urine pregnancy test within 3 days prior to commencing trial treatment and this test should be repeated prior to trial treatment on Day 1 of the WOP and at the 30 day post-surgery visit.
- 5. Trial-specific imaging: should be performed at least 1 week following day 1 of the final cycle of NACT and will be used to confirm that the residual disease is ≥ 1cm in order to confirm eligibility for Trial Entry.
- 6. **Assessment of Adverse Events:** SAEs should be followed up until resolution.
- 7. Review of potential Drug-Drug Interactions (DDI) with anaesthetics: Please refer to Appendix 6.
- 8. **Research Core Biopsy:** A minimum of four and up to a maximum of 8 core biopsies should be collected. The number of cores to be collected should be decided on a case-by-case basis by the radiologist at the time of collection, with the aim of ensuring that at least 4 high quality tissue cores are obtained. Please refer to the PHOENIX Investigator Laboratory Manual for further instruction. *In exceptional cases when the collection of the biopsy on Day 14 is not feasible then image-guided research biopsy cores can be collected on the day of surgery or taken by the surgeon intraoperatively, with the time from the Day 14 assessments to biopsy minimised and recorded.*
- 9. **Research Blood Sample Collection:** Please refer to the PHOENIX Investigator Laboratory Manual for further instruction.
- 10. Peripheral Blood Mononuclear Cell (PBMC) Isolation Blood Sample Collection: Sites geographically located in order for the sample to be couriered to the PHOENIX Central Laboratory for same day processing will be required to collect PBMC isolation blood samples from all patients. Where possible, blood for PBMC isolation should be collected in the morning to allow for prompt shipment and processing within the required time-frame. Please refer to the PHOENIX Investigator Laboratory Manual for further instruction.
- 11. **Surgical Resection:** Residual Cancer Burden (RCB) should be assessed from surgical resection tissue for each PHOENIX patient. For instructions on how to calculate RCB and the parameters required, please refer to Appendix 2.
- 12. **Timing of Surgery in relation to WOP:** The optimal trial schedule is for surgery to take place within 24 hours of the D14 WOP visit. However, surgery can take place up to 3 days following the D14 WOP visit to allow patients to self-isolate prior to surgery if required as part of national or local guidelines.
- 13. Trial treatment in Part 2: Eligible patients allocated to Cohorts F and G will be invited to receive further trial treatment in Part 2. Provision of the Part 2 Trial Treatment Patient Information Sheet to the patient should be as soon as possible following confirmation of cohort allocation with patients being invited to consent at the 30-day post-surgical resection visit.

### 12. SELECTION OF PATIENTS FOR TRIAL TREATMENT IN PART 2

All patients consent to follow-up after surgery at the time of Trial Entry. Trial pathway in Part 2 is dependent on cohort allocation i.e. HRD and gBRCA1/2 mutation status, and whether a patient is eligible and consents to further trial treatment in Part 2:

- Patients allocated to Cohort E (gBRCA1/2m negative and non-HRD), and patients allocated to either Cohort F or G who are ineligible for or non-consenting to further trial treatment, will receive SOC adjuvant treatment of Physician's Choice with 3 monthly follow-up and ctDNA blood sampling visits (Section 14)
- Patients allocated to either Cohort F or Cohort G, who consent to and are eligible for trial treatment
  in Part 2 will receive olaparib and durvalumab in combination for 12 months with 4 weekly safety
  and ctDNA blood sampling visits. This will be followed by a further 12 months of 3 monthly followup and ctDNA blood sampling visits (Section 13). Patients who are found to be ineligible for
  durvalumab treatment will receive olaparib only.

Patients may be offered adjuvant radiotherapy following surgery if clinically indicated. Radiotherapy should be delivered according to local practice and must be completed at least three weeks prior to commencement of any trial treatment in PART 2. If a patient receives radiotherapy as SOC, this information must be recorded in the patient's notes, as well as in the appropriate eCRF pages within the PHOENIX database.

Patients who are receiving SOC pembrolizumab will be required to discontinue this treatment following consent to Part 2 Trial Treatment and prior to commencing trial treatment, and details relating to this are included in the Part 2 Trial Treatment Patient Information Sheet. The washout period required between discontinuation of pembrolizumab and day 1 cycle 1 of durvalumab is 30 days and further details are included in Section 12.3 below. Patients who are unwilling to discontinue pembrolizumab should not be invited to consent to Trial Treatment in Part 2 and instead receive SOC treatment of Physician's Choice (including continued pembrolizumab) and followed up as detailed in Section 14.

Patients whose clinical management includes the use of adjuvant capecitabine will not be invited to receive further trial treatment in PART 2 of the trial, but will be followed up every 3 months with ctDNA blood sampling for a total of 24 months as detailed in Section 14.

In order to receive trial treatment in Part 2 the patient must meet all trial entry eligibility criteria provided below.

### 12.1. Eligibility Criteria for Trial Treatment in Part 2 - Cohorts F & G only

As all patients receive olaparib during the post-neoadjuvant treatment and pre-surgical 14-day WOP, fulfilment of eligibility criteria for olaparib treatment is confirmed at the time of Trial Entry. To determine eligibility for further olaparib trial treatment in Part 2, pre-treatment assessments will include repeat physical examination and assessments of vital signs, ECOG performance status, and safety bloods as detailed in Section 13.1. These pre-treatment assessments should be used to determine fulfilment of the eligibility criteria for further olaparib treatment in Part 2 included in Section 12.1.1 below. Any patients who experienced unacceptable toxicity as judged by the investigator and/or discontinued olaparib treatment during the WOP should not be invited to consent to further trial treatment in Part 2, and should receive SOC treatment of Physician's Choice and followed up as described in Section 14.

IRAS Project Number: 249774

Patients who remain eligible for further olaparib treatment in Part 2, must fulfil the exclusion criteria for durvalumab listed below (Section 12.1.2) to receive olaparib and durvalumab combination therapy otherwise they will receive olaparib alone (Section 12.1.3):

### 12.1.1. Inclusion Criteria for trial treatment in Part 2

- 1. Eastern Oncology Cooperative Group (ECOG) performance status 0-1;
- 2. Confirmation of residual disease following primary surgery as per local pathology reporting;
- 3. Patients must have adequate haematological, renal and hepatic function as defined by:
  - Haemoglobin (Hb) ≥ 10 g/dL (≥ 100 g/L)
  - Absolute neutrophil count (ANC)  $\geq 1500/\text{mm}^3$  ( $\geq 1.5 \times 10^9/\text{L}$ )
  - Platelet count ≥100,000/mm³ (≥ 100 x 109/L)
  - Total bilirubin ≤ 1.5 x institutional upper limit of normal (ULN)
  - Aspartate aminotransferase (AST) (Serum Glutamic Oxaloacetic Transaminase (SGOT)) / Alanine aminotransferase (ALT) (Serum Glutamic Pyruvate Transaminase (SGPT))  $\leq$  2.5 x institutional ULN
  - Calculated creatinine clearance ≥51 mL/min using the Cockcroft-Gault equation (please refer to Appendix 4) or based on a 24 hour urine test or another validated test as per local practice

### 12.1.2. Exclusion Criteria for durvalumab treatment in Part 2

- 1. Body weight  $\leq$  30kg.
- 2. Patients who have received prior pembrolizumab:
  - a) Must not have experienced a toxicity that led to permanent discontinuation of prior immunotherapy.
  - b) All immunotherapy-related AEs while receiving prior pembrolizumab must have completely resolved or resolved to baseline prior to screening *for eligibility for Part 2 durvalumab treatment*.
  - c) Must not have experienced a ≥Grade 3 immune related AE or an immune related neurologic or ocular AE of any grade while receiving prior immunotherapy. NOTE: Patients with endocrine AE of ≤Grade 2 are eligible for durvalumab if they are stably maintained on appropriate replacement therapy and are asymptomatic.
  - d) Must not have required the use of additional immunosuppression other than corticosteroids for the management of an AE, not have experienced recurrence of an AE if re-challenged, and not currently require maintenance doses of > 10 mg prednisone or equivalent per day.
- Patients receiving, or having received pembrolizumab must have a minimum washout period of 30 days from last dose of pembrolizumab and Day 1 Cycle 1 of durvalumab trial treatment (see Section 12.3 for details).
- 4. Radiotherapy treatment to more than 30% of the bone marrow or with a wide field of radiation within 4 weeks of the first dose of durvalumab
- 5. History of allogenic organ transplantation.
- 6. Active or prior documented autoimmune or inflammatory disorders (including inflammatory bowel disease [e.g., colitis or Crohn's disease], diverticulitis [with the exception of diverticulosis], systemic lupus erythematosus, Sarcoidosis syndrome, or Wegener syndrome [granulomatosis with polyangiitis,

Graves' disease, rheumatoid arthritis, hypophysitis, uveitis, etc]). The following are exceptions to this criterion:

- a. Patients with vitiligo or alopecia
- b. Patients with hypothyroidism (e.g., following Hashimoto syndrome) stable on hormone replacement
- c. Any chronic skin condition that does not require systemic therapy
- d. Patients without active disease in the last 5 years may be included but only after consultation with the Chief Investigator or Coordinating Investigator
- e. Patients with celiac disease controlled by diet alone
- 7. Current or prior use of immunosuppressive medication within 14 days before the first dose of durvalumab. The following are exceptions to this criterion:
  - a. Intranasal, inhaled, topical steroids, or local steroid injections (e.g., intra articular injection)
  - b. Systemic corticosteroids at physiologic doses not to exceed 10 mg/day of prednisone or its equivalent
  - c. Steroids as premedication for hypersensitivity reactions (e.g., CT scan premedication)
- 8. Receipt of live attenuated vaccine within 30 days prior to the first dose of durvalumab. Note: Patients who commence durvalumab therapy in Part 2 should not receive live vaccine whilst receiving durvalumab and up to 90 days after the last dose of durvalumab.
- 9. Known allergy or hypersensitivity to durvalumab or any excipient.

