#### Cohorts E-G

Patients allocated to Cohorts F & G will be invited to consent to further trial treatment in Part 2 at the 30 day visit. Eligible and consenting patients will receive trial olaparib and durvalumab combination therapy for a maximum of 12 months with 4 weekly follow-up and (optional) ctDNA blood sampling for 24 months. Patients that are not eligible for durvalumab will receive olaparib monotherapy.

Patients allocated to Cohort E, or those allocated to Cohorts F or G and non-consenting or not eligible for trial treatment in part 2, will receive (SOC) treatment of physician's choice with 3-monthly follow-up with (optional) ctDNA blood sampling for 24 months.

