- 15. Patients with a known hypersensitivity to pembrolizumab, durvalumab or olaparib or any excipients of the products;
- 16. Previous allogenic bone marrow transplant or double umbilical cord blood transplantation (dUCBT);
- 17. Active infection including tuberculosis (TB) (clinical evaluation that includes clinical history, physical examination and radiographic findings, and TB testing in line with local practice), hepatitis B (HBV; known positive HBV surface antigen (HBsAg) result), hepatitis C (HCV), or human immunodeficiency virus (HIV; positive HIV 1/2 antibodies). Patients with a past or resolved HBV infection (defined as the presence of hepatitis B core antibody [anti-HBc] and absence of HBsAg) are eligible. Patients positive for HCV antibody are eligible only if polymerase chain reaction is negative for HCV RNA;

Please note, the following exclusion criteria will apply prior to Trial Entry. These criteria should be considered prior to Trial Registration with the expectation that the patient would not be excluded from Trial Entry based on these points:

- 1. History of clinically significant or uncontrolled cardiovascular disease including:
  - Myocardial infarction within 6 months prior to Trial Entry;
  - Uncontrolled angina within 3 months prior to Trial Entry;
  - Congestive heart failure New York Heart Association (NYHA) class III or IV, or patients with history of congestive heart failure NYHA class III or IV in the past, unless an echocardiogram (ECHO) or multi-gated acquisition (MUGA) scan performed within 3 months prior to Trial Entry results in a left ventricular ejection fraction that is 45%;
  - History of clinically significant ventricular arrhythmias (e.g. ventricular tachycardia, ventricular fibrillation, torsades de pointes);
  - History of Mobitz II second degree or third degree heart block without a permanent pacemaker in place;
  - Consistent evidence of hypotension as indicated by systolic blood pressure < 90 millimeters of mercury (mm Hg) prior to Trial Entry;
  - Consistent evidence of bradycardia as indicated by a heart rate of < 50 beats per minute on the ECG prior to Trial Entry;

IRAS Project Number: 249774

- Consistent evidence of uncontrolled hypertension as indicated by systolic blood pressure >
   170 mm Hg or diastolic blood pressure > 105 mm Hg prior to Trial Entry.
- 2. History of loss of consciousness or transient ischemic attack within 12 months prior to Trial Entry;

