### 12.1.3. Part 2 trial treatment for patients ineligible for durvalumab treatment

Patients who do not fulfil eligibility criteria above for durvalumab treatment, and who remain eligible for olaparib, should receive olaparib monotherapy for 12 months (13 cycles) during Part 2.

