### 12.2.1. Non-consenting Patients from Cohorts F & G

Patients who do not consent to, or who are ineligible for, trial treatment in Part 2 should receive adjuvant treatment of Physician's Choice and followed up as described in Section 14.

# 12.3. Pembrolizumab treatment washout period requirement for patients eligible to receive durvalumab treatment in Part 2

Patients who are receiving pembrolizumab as part of standard of care, and who fulfil the eligibility criteria for durvalumab treatment in Part 2, should be asked to discontinue pembrolizumab only once consent to trial treatment in Part 2 has been obtained. The minimum washout period between last dose of pembrolizumab and Cycle 1 Day 1 of durvalumab is 30 days. Details relating to treatment with pembrolizumab, including date of last dose, will be captured in on the appropriate eCRF within the clinical database.

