# SECTION 25 PART 2: OLAPARIB AND DURVALUMAB COMBINATION THERAPY TRIAL TREATMENT INFORMATION COHORTS F & G

# 25. PART 2 OLAPARIB AND DURVALUMAB COMBINATION THERAPY: TRIAL TREATMENT INFORMATION COHORTS F & G

#### 25.1. Part 2 Trial Treatment

Olaparib and durvalumab are the IMP for Cohorts F & G in Part 2 of the trial. Eligible patients will receive olaparib and durvalumab combination therapy. Patients who are not eligible for durvalumab treatment can receive olaparib monotherapy.

For patients that are receiving pembrolizumab as SOC the washout period from last dose of pembrolizumab and start of durvalumab is 30 days. Further details can be found in Section 12.3.

Trial treatment details for olaparib and durvalumab are shown separately below. The Investigator should use clinical judgement when attributing a toxicity to olaparib or durvalumab when given in combination. The choice of toxicity management guidelines should be based on the investigator's assessment of the causal role of the individual IMPs. In situations where the assessment qualifies both IMP toxicity management guidelines for a particular toxicity, the more conservative dose modification and/or dose interruption should be applied.

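### Section 12.1 ties the durvalumab combination to fulfilling a list of exclusion criteria, which points the wrong way for seven of the list's twelve conditions

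*Protocol*

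**What the plan says.** Section 12.1 of the Protocol sets out how Part 2 treatment is chosen in Cohorts F and G. Patients who remain eligible for olaparib "must fulfil the exclusion criteria for durvalumab listed below (Section 12.1.2) to receive olaparib and durvalumab combination therapy otherwise they will receive olaparib alone". The sentence sends the first group to Section 12.1.2, which is headed as a list of exclusion criteria for durvalumab, and the second group to Section 12.1.3.

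Section 12.1.3 states the rule from the other side: "Patients who do not fulfil eligibility criteria above for durvalumab treatment, and who remain eligible for olaparib, should receive olaparib monotherapy". Section 12.3, on the pembrolizumab washout, describes those due to receive durvalumab as patients on standard-of-care pembrolizumab "and who fulfil the eligibility criteria for durvalumab treatment in Part 2".

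Three other places describe the same allocation in general terms:
- Section 3 (Trial Design, Part 2, Cohorts E-G): "Patients that are not eligible for durvalumab will receive olaparib monotherapy".
- Section 12: patients found ineligible for "durvalumab treatment will receive olaparib only".
- Section 25.1: "Patients who are not eligible for durvalumab treatment can receive olaparib monotherapy".

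**The concern.** An exclusion criterion is ordinarily something a patient must not meet. Section 12.1 makes meeting the exclusion criteria the condition for receiving durvalumab and sends everyone else to olaparib alone. For a patient with, say, a past organ transplant, the literal text leads to the checkpoint inhibitor instead of away from it.

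This is not background text. It is the operative rule that assigns combination or monotherapy in Part 2, and the conditions it governs are safety conditions. Section 12.2 requires the site to document that the patient meets all the Part 2 eligibility criteria. A checklist copied from 12.1 and 12.1.2 as they stand would mix questions where yes means eligible with questions where yes means ineligible.

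**Working it through.** No arithmetic is needed beyond a count. The check is to take each condition in Section 12.1.2, apply the verb in Section 12.1 to it, and compare the result with Section 12.1.3.

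**Step 1. Polarity of each condition in 12.1.2**

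| Item | Content, in short | Written as | Effect of *must fulfil* |
|---|---|---|---|
| 1 | body weight of 30 kg or less | contraindication | wrong direction |
| 2a | no toxicity that permanently stopped prior immunotherapy | requirement | correct |
| 2b | immunotherapy-related events resolved or back to baseline | requirement | correct |
| 2c | no grade 3 or worse immune-related event, and no neurologic or ocular one of any grade | requirement | correct |
| 2d | no immunosuppression beyond corticosteroids, no recurrence on re-challenge, no maintenance above 10 mg prednisone | requirement | correct |
| 3 | at least 30 days since last pembrolizumab | requirement | correct |
| 4 | recent extensive radiotherapy | contraindication | wrong direction |
| 5 | organ transplantation | contraindication | wrong direction |
| 6 | autoimmune or inflammatory disorder | contraindication | wrong direction |
| 7 | immunosuppressive medication within 14 days | contraindication | wrong direction |
| 8 | live vaccine within 30 days | contraindication | wrong direction |
| 9 | "Known allergy or hypersensitivity to durvalumab or any excipient" | contraindication | wrong direction |

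Contraindications: 1, 4, 5, 6, 7, 8, 9 = 7. Requirements: 2a, 2b, 2c, 2d, 3 = 5. Total 7 + 5 = 12.

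**Step 2. Comparison with the neighbouring text**

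The heading of 12.1.2 says the list excludes, while 12.1 uses it to include. Section 12.1.3 uses the same verb but attaches it to eligibility criteria and sends those who do not fulfil them to monotherapy. That is the opposite of 12.1 for the seven contraindications and the same as 12.1 for the five requirements.

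Sections 3, 12, 12.3 and 25.1 speak only of being eligible or ineligible for durvalumab, or of fulfilling eligibility criteria, without saying what makes a patient so. They conflict with 12.1 only through the ordinary meaning of eligible, and support the intended direction to that extent. For an exclusion list elsewhere, the Protocol uses the usual form: Trial Entry exclusion 8 (Section 8.1.2) asks for confirmation that no Registration exclusion is met.

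**Step 3. Would a one-word repair do?**

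Changing 12.1 to say that patients must meet none of the criteria in 12.1.2 would correct items 1 and 4 to 9 but reverse 2a to 2d and 3. A patient who had completed the washout would then fail. No single verb suits the list as written, so the sentence and the list need to be corrected together.

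**Step 4. Who and what is affected**

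Section 5.1 caps Part 2 trial treatment at 23 patients, which is 8 in Cohort F plus 15 in Cohort G. The Part 1 designs in Section 17.1.1 rest on responses in the preoperative olaparib window, before this rule applies. Section 17.1.2 describes Part 2 as exploratory. No power, error rate or stopping boundary changes.

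**The case against.** The strongest reply is that this is loose shorthand for satisfying Section 12.1.2 and that no site would be misled. The sentence cites a list headed as exclusions and sends the remainder to a section headed for patients ineligible for durvalumab, so either cross-reference leads to the right rule. Each item in 12.1.2 is clear on its own, and replacing one word, *exclusion* by *eligibility*, would bring 12.1 into line with 12.1.3. Most of this stands: the intent is recoverable, and nothing in the Protocol shows that a patient was or would be misassigned. It does not make the sentence right, and the one-word change would still point to a list of mixed polarity under an exclusion heading.

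Stronger readings are tempting, but the documents do not support them.
- A reader might infer that the whole durvalumab rule is inverted. Five of the twelve conditions already read correctly.
- A reader might infer that the literal rule admits nobody, because item 9 would demand a hypersensitivity that Registration exclusion 15 already bars: "Patients with a known hypersensitivity to pembrolizumab, durvalumab or olaparib or any excipients of the products". That requires reading the sentence as asking for every item at once and assuming that no hypersensitivity becomes known after Registration. If any one item sufficed, contraindicated patients would qualify instead. The text does not choose between these readings.
- A reader might infer that a careless repair would remove all trace of the prior-pembrolizumab safeguards. The 10 mg steroid limit in 2d also appears in item 7b and Section 25.3.8, and the washout in item 3 is repeated in Sections 12, 12.3, 13.1.2 and 25.1.

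**Conclusion.** The point holds as a low-severity wording error in an operative safety rule. Section 12.1 has the wrong direction for items 1 and 4 to 9 of Section 12.1.2, and it conflicts with that section's heading and with Section 12.1.3. It reads correctly for items 2a to 2d and 3.

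The size is one sentence and one list of mixed polarity, bearing on the treatment of at most 23 patients in a descriptive part of the trial. The low rating rests on two things: sites would take the intended rule from 12.1.3 and from the items themselves, and no trial inference depends on the allocation. It is still worth correcting, because following the sentence literally for a contraindicated item gives the wrong treatment.

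**What to change.** In Section 12.1, state that the combination is given only if none of items 1 and 4 to 9 of Section 12.1.2 applies and, for patients with prior pembrolizumab, conditions 2a to 2d and 3 are satisfied. All others who remain eligible for olaparib receive olaparib alone.

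In Section 12.1.2, either reword 2a to 2d and 3 as exclusions, so that the list has one polarity, or move them to a short durvalumab inclusion list. Make this change together with the one in 12.1. Then check that the PART 2 Trial Treatment Form named in Section 12.2 follows the same direction.

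The cost is protocol wording at the next amendment and a check of one form. No clinical threshold, sample size or analysis changes.
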